#### 3.1.6 Handling missing data

In general, other than for partial dates, missing data will not be imputed and will be treated as missing, with some exceptions specified for certain efficacy variables.

The main analysis for change from baseline specified for primary and secondary endpoints in following sections will use the repeated measures model. There will be no imputations used for missing values for the primary analysis data. There will be four sensitivity analyses, as described below, which will look at the effect of missingness.

- For patients who started rescue medication or terminated the study medication, a sensitivity analysis will be performed using the same MMRM model as the primary analysis where only measurements taken prior to the date of the first dose of rescue medication or up to 8 days post the last dose date of the study medication will be used. This model assumes that the time course of the endpoint values for patients who discontinue treatment or are rescued at a specified time point is consistent with the time course for patients who are ongoing at that time point.
- 2) A tipping point sensitivity analysis using ANCOVA for the primary endpoint at week 24 that will use the delta-adjustment method to impute missing data via the multiple imputation method within the pattern-mixture model [1].

A sensitivity analysis will be done which utilizes ANCOVA for the primary endpoint at week 24 with a multiple imputation that makes a not missing at random (NMAR) assumption for missing data from subjects who discontinued treatment. Multiple imputation models will be built separately for each arm which utilize only the data from subjects who discontinued treatment but still obtained the week 24 endpoint assessment (called MI-RD). The delta adjustment method uses the assumption that patients from the main treatment arm of interest (saxagliptin 5mg co-administered with dapagliflozin 5mg added to metformin) who discontinue treatment would have, on average, their unobserved HbA1c at week 24 worse by some amount compared with the observed HbA1c at week 24 of similar patients that continue treatment. Patients who discontinue from the control arms (saxagliptin 5mg or dapagliflozin 5mg added to metformin) would exhibit the same evolution of the disease as similar control patients that stay on study.

Using these assumptions we can define 4 groups of patients with regards to observed data and patterns of missingness. The control patients refer to saxagliptin 5mg or dapagliflozin 5mg added to metformin patients, and the experimental arm patients refer to saxagliptin 5mg + dapagliflozin 5mg + metformin patients.

At each time-point t, consider four groups of patients:

- (P1) control patients with assessment observed at time-point t
- (P2) pattern of control patients with missing assessment at time-point t
- (P3) experimental arm patients with assessment observed at time-point t
- (P4) pattern of experimental arm patients with missing assessment at time-point t

Observed data (P1) serves as a model for the pattern (P2) such that the imputation model estimated within (P1) is used without any changes to draw imputations for patients in pattern (P2). Observed data (P3) would serve as a basis for a model for the pattern (P4). However, predictions from the model estimated within (P3) would be altered before being imputed for patients in (P4). Specifically, the predicted values would be worsened by a pre-fixed value,  $\delta$ , ( $\delta$  adjustment strategy) using a regression based multiple imputation method, at week 24. This would reflect an assumption that patients who drop out from the experimental arm would do worse after dropout than otherwise predicted by their observed outcomes and covariates.

The tipping point analysis will be performed as follows if the primary analysis is statistically significant:

- 1. The missing data should first be imputed assuming MAR with the delta being added the week 24 endpoint.
- 2. Run the delta-adjustment method using a binary search (or other appropriate algorithm) to select the value of delta which yields a p-value exactly equal to 0.05.
- 3. Also report the analysis results for delta values with p-values equal to 0.01 and 0.025.

The multiple imputation sensitivity analysis will build three separate multiple imputation models using the regression method for monotone missing data. Nonmonotone missing data

Statistical Analysis Plan Amendment Study Code D1683C00005 Edition Number 4.0 Date 09th Aug 2017 should be imputed using the Markov Chain Monte Carlo (MCMC) method prior to using the regression method. The data used in the imputation model will be restricted to only those subjects who have discontinued treatment but have the primary endpoint available at week 24.

The secondary efficacy variable of proportion of patients achieving a therapeutic glycaemic response is defined as having HbA1c <7.0% at Week 24. Patients who did not have A1c measurement at week 24 will be treated as those who did not to achieve a therapeutic glycaemic response.

#### 3.1.6.1 Imputation of partial dates

#### **Concomitant Medication Dates**

Imputation of start dates allows medications for subjects to be classified into the categories of prior, concomitant (or both) for tables. An assessment should be made as to the possibility that the subject's medication could fall into each category given the information available for the dates. If it is possible given the date information that a subject's medication could fall into a given category, then the subjects' medication should be included for tables for that category. If a particular category can be ruled out based on partial or full dates available, then the subject's medication should be excluded from that category. The following date imputation should accomplish this:

#### Start Dates

- If year is missing (or the date is completely missing), set start date equal to the consent date.
- If (year is present and month and/or day are missing then impute start date as the earliest possible date given the partially entered date, i.e. first day of month, or first day of first month.
- If the resulting imputed start date is after a non-missing (i.e. not imputed) end date then set the start date equal to the end date.

#### End Dates

- If year is missing (or the date is completely missing) set end date equal to the latest database extraction date.
- If the year is known but month and/or day is missing, then set end date equal to the latest known date for this patient unless it is after the concomitant med start date (actual or imputed). If it is before the concomitant med start date then set it equal to the concomitant med start date.

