If all dates used to determine the surrogate date are missing, then based on the information provided, set the derived date to the earliest possible date. If only a year is provided, set the derived date to January first of that year. If a year and month is provided, set the derived date to the first day of that month.

End Dates

Statistical Analysis Plan Amendment Study Code D1683C00005 Edition Number 4.0 Date 09th Aug 2017 A missing or incomplete end date of an AE will be imputed according to the following conventions:

- If an end date is missing, the derived end date will be set to missing
- If an end date is incomplete, set the derived end date to be the latest possible date based on the partial onset date information provided. If only a year is provided, set the derived date to December 31st of that year. If a year and month is provided, set the derived date to the last day of that month.

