#### 4.2.2.4 **Prior Medications**

Previous medications, including any medication (other than study medications) with a start date prior to Day 1 of treatment period, will be summarized.

Missing and partial date handling of start and stop dates of previous medications is described in Section 3.1.6.1 above. The AZ Drug Dictionary v16.1is used to code the non-study medication.

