#### 4.2.3.2 Extent of Exposure – Concomitant Medications

Concomitant medications include any medication taken from start of the treatment period up to the end of the treatment period.

Concomitant medications will be summarized using the SAF dataset by drug class and (generic) drug name. A summary table by drug class and generic drug name will be generated for each of the following:

- all concomitant medication
- all concomitant diuretic medication
- all concomitant anti-hypertensive medication

To identify each type of diuretic medication and anti-hypertensive medication a list of terms will be selected before database lock and unblinding of the database. Missing and partial date handling of start and stop dates of concomitant medications is described in Section 3.1.6.1 above.

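### The rule for partial medication end dates ignores the recorded year and month, so a drug that stopped before Day 1 is counted as concomitant

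*SAP*

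**What the plan says.** SAP section 3.1.6.1 (Concomitant Medication Dates) starts from a two-way principle. A medication goes into the prior or concomitant category if its dates make that possible. The reverse also holds: "If a particular category can be ruled out based on partial or full dates available, then the subject's medication should be excluded from that category". Next, the SAP introduces its imputation bullets with the words "The following date imputation should accomplish this".

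The bullet for an end date with a known year and a missing month and/or day says to "set end date equal to the latest known date for this patient unless it is after the concomitant med start date". The next sentence adds: "If it is before the concomitant med start date then set it equal to the concomitant med start date". Nothing else constrains the imputed date.

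Two neighbouring rules do use the recorded part of a date. For a partial medication start date the SAP says to "impute start date as the earliest possible date given the partially entered date". For an incomplete adverse event end date it says to "set the derived end date to be the latest possible date based on the partial onset date information provided", and it spells this out as the last day of the month or 31 December.

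SAP section 4.2.3.2 counts a drug as concomitant if it was taken at any time in the treatment period. On dates it says: "Missing and partial date handling of start and stop dates of concomitant medications is described in" section 3.1.6.1. SAP section 4.2.2.4 defines prior medications by start date alone, as those "with a start date prior to Day 1 of treatment period, will be summarized".

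**The concern.** The end-date bullet discards information that the site recorded. If the entry shows only that a drug ended in a month or year lying wholly before Day 1, concomitant use is ruled out. The bullet nevertheless moves the end date to the patient's last known date, which for a treated patient is on or after Day 1. The drug then passes the concomitant test, against the principle the bullet is meant to implement.

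The sentence also contains a slip. Read literally, *unless it is after* the drug's start switches the rule off in the ordinary case, because a patient's latest known date normally is after the start of the drug. No end date is then assigned. The following sentence shows that *before* was meant.

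At stake is one yes/no classification per drug. Drugs already stopped are added to the concomitant-medication tables (all, diuretic, anti-hypertensive). The prior-medication summary does not change, so such a drug appears as both prior and concomitant when it should appear only as prior.

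**Working it through.** There is no stated figure to reproduce, so the check applies the rule to example records.

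**Assumed dates (not from the documents).** Enrolment is on 2 May 2016 and the drug started before 2015. With the Protocol Table 1 intervals:
- Day 1 = 2 May 2016 + 14 days = 16 May 2016.
- Visit 5 = 16 May 2016 + 168 days = 31 October 2016, taken as the patient's latest known date.

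**Rules compared.**
- SAP rule as evidently intended: end = latest known date, or the start date if that is later.
- Latest possible date: end = last day of the recorded month, or 31 December of the recorded year, capped at the latest known date and not before the start date.
- Concomitant (SAP 4.2.3.2), for a drug started before Day 1: end on or after Day 1.

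| Recorded end | SAP rule gives | Concomitant? | Latest possible date | Concomitant possible? |
|---|---|---|---|---|
| 2015 | 31 Oct 2016 | yes | 31 Dec 2015 (137 days before Day 1) | no |
| Feb 2016 | 31 Oct 2016 | yes | 29 Feb 2016 (77 days before) | no |
| Mar 2016 | 31 Oct 2016 | yes | 31 Mar 2016 (46 days before) | no |
| Apr 2016 | 31 Oct 2016 | yes | 30 Apr 2016 (16 days before) | no |
| May 2016 | 31 Oct 2016 | yes | 31 May 2016 | yes |
| 2016 | 31 Oct 2016 | yes | 31 Dec 2016, capped at 31 Oct 2016 | yes |

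The day counts run back from 16 May: April to May is 16; adding 30 for April gives 46; adding 31 for March gives 77; adding 29 for February and 31 for January gives 137.

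The SAP rule classes 6 of 6 as concomitant, and the SAP's own principle allows 2 of 6. On the literal wording none of the six receives an end date, because 31 October 2016 is after the drug's start.

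**Can such records arise?** Protocol section 4.2.1 has prescription medications from the previous 3 months reviewed at enrolment, here from about 2 February 2016. Every day of March and April 2016 lies inside that window. February is at its edge and 2015 is outside it, so the March and April rows carry the illustration.

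**Check with the start year also missing.** The SAP sets the start to the consent date, here 2 May 2016. With end *Mar 2016*, the latest possible date of 31 March precedes the start, so the end becomes 2 May 2016. That is before Day 1, and the drug is still not concomitant.

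**The case against.** The strongest reply is that the governing principle already forbids the misclassification. The bullets are only a means to it, so a careful programmer would exclude these drugs. On that view this is loose drafting: the sentence already has one wrong word, and *latest possible date* may have been what was meant. That does not remove the conflict. The SAP says the bullets deliver the principle, and a programmer who follows them gets the opposite result. The text also speaks of the patient's latest known date, not the latest date the entry allows, and the SAP words that second idea differently and explicitly elsewhere.

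Several narrower points stand:
- The SAP's adverse event rule is not a clean model, since its sentence on end dates refers to partial *onset* information. That is a separate slip and does not touch the wording proposed below.
- The six records were chosen to show the rule at work. The contrast of 6 with 2 says nothing about frequency.
- Data queries under Protocol section 9.4 should reduce the number of partial dates.
- The error can only over-include, and only in tables for which SAP section 4.2.3.2 plans no test.

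Over-inclusion is not a defence where use during treatment is ruled out, because the SAP asks for exclusion in exactly that case.

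**Conclusion.** The concern holds, at minor severity. As written, the rule for partial medication end dates contradicts the principle it is meant to carry out. Read literally, it assigns no end date in the ordinary case. Read as intended, it makes every drug with a partial end date wholly before Day 1 concomitant.

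The conclusion rests on reading *after* as *before*, which the SAP's next sentence supports, and on taking the patient's latest known date at face value. The calendar dates in the example are assumed. The documents do not give the number of affected records, so no count is offered.

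The demonstrated effect is confined to the three descriptive concomitant-medication tables. No effect on the primary, secondary or per-protocol analyses is shown. The documents do not say whether imputed dates feed the per-protocol deviation for other glucose-lowering drugs (SAP Table 1, no. 9).

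**What to change.** Replace the second end-date bullet under Concomitant Medication Dates with:

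> If the year, or the year and month, of the end date is known, impute 31 December of that year or the last day of that month, capped at the patient's latest known date. If the result is before the start date (actual or imputed), set it to the start date.

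This keeps every drug that could have been taken during treatment: the latest known date of a treated patient is on or after Day 1, so the cap cannot remove one. It excludes drugs whose recorded end rules such use out, and it removes the faulty *unless* clause. While editing the section, correct *onset* to *end* in the sentence on incomplete adverse event end dates.

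The cost is one SAP sentence and a matching small change to the derivation code. No new data are needed.

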#### **Adverse Events Dates**

In case of missing dates, prior to assigning the treatment that the subject received at the onset of an AE or at the time of a laboratory assessment, imputation rules will be applied as follows:

If the onset date for an AE is missing or incomplete, an imputed date will be derived. This derived date will not be reported in summary tables or listings. Every effort will be made to determine the actual onset date for the event or to obtain a reliable estimate for the onset date from the investigator.

If an onset date is completely **missing** (or the year is missing), the **derived onset date** will be calculated as the first non-missing valid (actual) date from the following list (in order of precedence):

- First active study medication date
- Consent date
- If a valid non-missing date is not available for any of these dates, the derived onset date will be set to missing.

If an onset date is incomplete, the derived onset date will be calculated using the following algorithm:

Calculate a surrogate date as the first non-missing valid date from the following list (in order of precedence):

- First active study medication date
- Consent date
- If a valid non-missing date is not available for any of these dates, the surrogate date will be set to missing.

Based on the information provided, set the initial derived date to the earliest possible date. If only a year is provided, set the derived date to January first of that year. If a year and month is provided, set the derived date to the first day of that month.

If the surrogate date is non-missing then:

- If the derived date is on or after the surrogate date use the derived date as calculated
- If the derived date is prior to the surrogate date and the surrogate date is consistent with the partial data provided for the onset date, use the surrogate date as the derived date
- If the derived date is prior to the surrogate date and the surrogate date is not consistent with the partial data provided for the onset date then set the derived onset date to be the latest possible date based on the partial onset date information provided. If only a year is provided, set the derived date to December 31st of that year. If a year and month is provided, set the derived date to the last day of that month.

If all dates used to determine the surrogate date are missing, then based on the information provided, set the derived date to the earliest possible date. If only a year is provided, set the derived date to January first of that year. If a year and month is provided, set the derived date to the first day of that month.

End Dates

Statistical Analysis Plan Amendment Study Code D1683C00005 Edition Number 4.0 Date 09th Aug 2017 A missing or incomplete end date of an AE will be imputed according to the following conventions:

- If an end date is missing, the derived end date will be set to missing
- If an end date is incomplete, set the derived end date to be the latest possible date based on the partial onset date information provided. If only a year is provided, set the derived date to December 31st of that year. If a year and month is provided, set the derived date to the last day of that month.

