# 6.3 Recording of adverse events

## 6.3.1 Time period for collection of adverse events

AEs will be collected from time of signature of informed consent, during the Enrolment, Randomisation, and throughout the treatment period and until End of treatment (Visit 5)/early termination.

SAEs will be recorded from the time of informed consent.

All AEs/SAEs will be recorded on source documents and the eCRFs.

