#### **All Adverse Events**

An overall summary of adverse events at patient level, including patients who experienced at least one: AE, hypoglycaemic event, treatment-related AE, death, SAE, treatment-related SAE, SAE leading to the discontinuation of study medication, hypoglycaemic event leading to the discontinuation of study medication, and AESI. All AEs (serious and non-serious, excluding hypoglycemic events that are not reported as SAEs) will be summarized by SOC and PT. In addition, a patient listing of all reported AEs will be produced, displaying all events that occurred prior to the start date of treatment period, if any. All AEs (serious and non-serious) including all hypoglycemic events will also be summarized by treatment group, where applicable.

Adverse events and SAEs with an onset from Day 1 of treatment up to and including 4 days and 30 days respectively, after the last dose date in the treatment period will be considered as occurring during the treatment period.

In addition, the following summaries will be provided for the treatment period (excluding hypoglycemic events that are not reported as SAEs):

- Most common adverse events by preferred term and treatment group (i.e., reported by  $\geq 2$  % of patients in any treatment group),
- Adverse events by system organ class, preferred term, intensity and treatment group,
- Adverse events related to study medication by system organ class, preferred term and treatment group.
- Proportion of patients with adverse events by SOC and PT in subgroups of patients defined by age category (< 65 and ≥ 65 years), gender and race.

No formal comparisons will be made between treatments. No formal statistical testing will be performed, only summary statistics will be provided.

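### The AE onset imputation ignores a recorded end date, so an event with a missing or compatible partial onset that ended before the first dose is counted on Day 1

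*SAP*

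**What the plan says.** All the imputation rules are in SAP 3.1.6.1 (Imputation of partial dates).

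- **AE onset wholly missing, or year missing.** The derived onset is "calculated as the first non-missing valid (actual) date from the following list (in order of precedence"). The first entry in that list is "First active study medication date"; the consent date comes second.
- **AE onset incomplete.** The first-dose date, when available, is the surrogate date. The onset is provisionally set to the earliest date that the partial information allows. If that is earlier than the surrogate and "the surrogate date is consistent with the partial data provided for the onset date, use the surrogate date as the derived date". If the surrogate does not fit the partial information, "then set the derived onset date to be the latest possible date based on the partial onset date information provided".
- **AE end date incomplete.** The instruction is to "set the derived end date to be the latest possible date based on the partial onset date information provided". A missing end date stays missing.
- **Medication start dates.** These carry a check that the AE rules lack: "If the resulting imputed start date is after a non-missing (i.e. not imputed) end date", the start date is set equal to the end date.

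Classification is in SAP 4.2.5.1. "Adverse events and SAEs with an onset from Day 1 of treatment" up to 4 days (AEs) or 30 days (SAEs) after the last dose belong to the treatment period, and the AESI paragraph repeats this. SAP 3.1.1 defines Day 1 as the first date of study treatment. Protocol 6.3.1 states that "AEs will be collected from time of signature of informed consent", so events before dosing are recorded.

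**The concern.** Defaulting an unknown onset to Day 1 is a sound cautious convention when nothing recorded contradicts it. Here the rule applies even when the recorded end date shows that the event was over before the first dose. The derived onset then falls after the event's own end, and an event that cannot have arisen on treatment enters the treatment-period tables.

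SAP 3.1.6.1 states the right principle for medications: where the available partial or full dates rule out a category, the record is left out of it. The medication start-date cap carries that out; the AE rules have no counterpart. Derived onset dates are not shown in tables or listings, so a reader of the tables would not see the reassignment. What is at stake is the accuracy of the by-arm AE, SAE and AESI counts. No efficacy analysis is touched.

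**Working it through.** The plan gives no figure on this point, so there is none to reproduce. The check applies the rules as written to test dates, then asks how often a pre-dose onset would be caught.

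**Test dates (illustrative), first dose 20 May 2016**

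| Recorded onset | Recorded end | Derived onset, current rule | In treatment period? | With end-date cap |
|---|---|---|---|---|
| May 2016, day missing | 12 May | 20 May (Day 1) | Yes | 12 May, not counted |
| 2016 only | 12 May | 20 May (Day 1) | Yes | 12 May, not counted |
| Wholly missing | 12 May | 20 May (Day 1) | Yes | 12 May, not counted |
| April 2016, day missing | any | 30 April | No | Not counted |
| 10 May 2016, complete | any | 10 May | No | Unchanged |

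Under SAP 3.1.1, 12 May is Study Day 12 − 20 = −8. The current rule thus places the onset 8 days after the recorded end.

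**How often a partial onset is compatible with the first-dose date**

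Inputs: Protocol Table 1, footnote d, puts Visit 2 at 14 ± 3 days after enrolment. Taking consent at Visit 1, the pre-dose window is L = 11, 14 or 17 days. The assumption, which is not in the documents, is that onsets are uniform over that window. The rules were run over 366 consecutive first-dose dates.

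For an onset with only the day missing, the chance of falling in the first-dose month is approximately 1 − (mean lag)/30.4.

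1. *All pre-dose events.* Mean lag = (L + 1)/2 = 6, 7.5 and 9 days. The formula gives 0.80, 0.75 and 0.70; enumeration gives 0.801, 0.751 and 0.702.
2. *Events that also ended before the first dose*, with every onset and end pair in the window equally likely. Mean onset lag = (2L + 1)/3 = 7.67, 9.67 and 11.67 days. The formula gives 0.75, 0.68 and 0.62; enumeration gives 0.746, 0.680 and 0.615.

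The second set describes the events at issue: with only the day missing, roughly 61% to 75% are moved to Day 1. When only the year is known, about 98% of all pre-dose onsets move. When the onset is wholly missing, all of them do. These shares are conditional on the onset being incomplete. The documents do not say how often that happens, so no count follows from them.

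**End-date rule**

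An event with onset April 2016 and end June 2016 gets a derived end of 30 April 2016 if the text is followed literally, which contradicts the recorded end month. Classification uses onset only, so the event's place in the tables does not change.

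**The case against.** The strongest reply is that the affected case is narrow and the plan has safeguards. The onset must be missing or compatible with the first-dose date, while the end date is known and earlier than the first dose; someone who can date the end of an event but not its start is unusual. SAP 3.1.6.1 promises every effort to obtain the actual onset or a reliable estimate. Protocol 6.3.3 requires start and stop dates, and Protocol 9.4 provides for queries on missing or inconsistent data. The rule is the same in all arms, AE summaries involve no formal testing, and any error overcounts treatment-period events, so it does not hide harm. All of this stands, and it limits the size of the problem. It does not correct the rule for an event whose date remains incomplete after querying.

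Three stronger readings are tempting, and the documents do not support them.

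- A reader might infer that every event that ended before dosing is moved to Day 1. Complete onsets are never altered. A partial onset from an earlier month or year goes to the last day of that month or year and stays before treatment.
- A reader might infer that the end-date wording adds to the miscount. SAP 4.2.5.1 classifies by onset alone and lists no AE-duration summary, so the derived end date feeds no stated table.
- A reader might take the 75% or 100% shares as the size of the effect. They cover all pre-dose events with an incomplete onset, including those still ongoing at first dose or with no end date. For those, Day 1 is a reasonable default, and the cap would change nothing.

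**Conclusion.** The point holds in a limited form. As written, an AE, SAE or AESI whose onset is missing, or partial and compatible with the first-dose date, is counted as a treatment-period event even when its recorded end date is before the first dose. This follows from the text alone and rests on no assumption. The shares in the working do rest on one, that onsets are uniform over an 11- to 17-day pre-dose window.

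The number of affected events is not in the documents. It is probably small, and the same rule applies in every arm. The practical consequence is confined to sparse SAE or AESI categories, where one misplaced event changes a by-arm count. The end-date wording is a separate drafting slip with no effect on classification.

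**What to change.** 1. Add the cap already used for medication start dates to both AE onset branches (missing and incomplete): if the recorded end date, or its latest possible date when it is partial, falls before the derived onset date, set the derived onset date to that end date. Where the end date is missing, or could still fall on or after the first dose, the Day 1 default stays.
2. As a drafting correction, change the AE end-date rule so that an incomplete end date is derived from the partial end date information instead of the partial onset date information.

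The cost is two sentences in SAP 3.1.6.1 and a small change to the AE derivation program. No data collection and no efficacy analysis is affected. Protocol 8.1 requires final SAP amendments before unblinding, so the change belongs there.
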